## **12. DISCONTINUATION FROM STUDY TREATMENT AND/OR STUDY WITHDRAWAL**

### **12.1 Discontinuation from study treatment**

A subject *must* permanently discontinue from Peg-IFN for any of the following reasons:

- The subject becomes pregnant.
- The subject withdraws consent.
- The subject experiences a medical emergency that necessitates permanent discontinuation of study treatment.
- At the discretion of the Investigator for medical reasons.
- At the discretion of the Investigator or Sponsor for noncompliance.
- Lost to follow up.

The reason for discontinuation from study treatment must be recorded in the subject's CRF.

All efforts must be made by the Investigator to perform the Early Termination Visit (ET visit) to Subjects discontinuing from treatment. However, the ET visit form will have to be filled by the investigator also for patients that are lost to follow up.

Subjects discontinuing from study treatment for any of the abovementioned reasons must be permanently withdrawn from the study.

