In addition, routine clinical assessments will be performed in order to check the safety of the Peg-IFN ongoing treatment.

Laboratory Safety Assessments

At the Investigator's discretion, the following routine laboratory tests can be carried out, in order to monitor the safety profile of the ongoing treatment based on Peg-IFN:

- Hematology: RBC- WBC –Haemoglobin- Haematocrit- MCV- MCH – MCHC - Platelets Count – Lymphocytes- Monocytes – Neutrophils – Eosinophils – Basophils
- Blood chemistry: creatinine, blood urea nitrogen (BUN), alkaline phosphatase, ALT, AST, gamma-glutamyl-transferase (GGT).

A pregnancy hCG test (blood sample) will be performed at the baseline visit (T0) to exclude pregnancy, if applicable (it is not required if the subject is post-menopausal or surgically sterilized).

9. Missing data

For missing data in TSQM-9, MSTCQ and MusiQoI see paragraph Variable of analysis.

For the other variables no imputation technique will be apply.

10. Statistical analysis

The primary and secondary endpoints will be evaluated using a repeated measures ANOVA. The repeated measures ANOVA is used to compare group means on a dependent variable across repeated measurements of time. This statistical method is used for making simultaneous comparisons between two or more means of two or more related, not independent, groups.

However, in addition, it could be useful to apply a general linear mixed model that models for group means as fixed effects while simultaneously modeling for individual subject variables as random effects (12). This kind of model is a subject-specific model and is a choice for analysing longitudinal data. Unlike the repeated measures ANOVA, which requires a complete balanced array of data, the mixed model can accommodate a dataset with a large portion missing. Although the repeated measures ANOVA requires a fixed time schedule among all individual units, the mixed model can accommodate flexible time schedules. Furthermore, rather than treating time as a categorical variable, as in the repeated measures ANOVA, the mixed model is capable of treating time as either a continuous variable or a categorical variable or both.

Spearman's correlation coefficient measures the strength of association between two ranked variables.

Differences will be considered statistically significant if the p-value will be less or equal to a type I error =0.05 (two-sided test).

11. Efficacy data

a. Primary Endpoint Analysis

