The primary endpoint is to evaluate the changes from baseline in the score of convenience satisfaction domain of TSQM-9 at 12 weeks. (*Stata instruction: anova var1 time, repeated(time)*)

b. Secondary Endpoints Analysis

- Changes from baseline in the score of all domains of TSQM-9 at 24 weeks;
- Changes from baseline in patient adherence to study treatment survey at 12 and 24 weeks;
- Changes from baseline in the score of FSS (Fatigue Status Scale) at 12 and 24 weeks;
- Changes from baseline in the score of Adapted Sclerosis Treatment Concerns Questionnaire (MSTCQ) at 12 and 24 weeks;
- Changes from baseline in the score of Multiple Sclerosis International Quality of Life questionnaire (MusiQoL) at 12 and 24 weeks;
- Changes from baseline in clinical measures (ARR, percentage of relapse-free patients), measures at 24 weeks.

All the above primary and secondary endpoints will be analysed by a repeated measures analysis of variance adjusted for baseline factors (age, sex, disease duration, previous treatment duration, EDSS) (*Stata instruction: anova var1 var2 time, repeated(time)*).

Correlations between variables will be assessed by a Spearman rank correlation coefficient (*Stata instruction: spearman var1 var2*).

[figure not shown]
To evaluate the relationship between patients' satisfaction and social-demographic factors (age, sex, employment working, level of education, etc.) and clinical characteristics (ARR, disability, etc.) generalized linear mixed models for repeated measurements will be performed (*Stata instruction: mixed var1 var2 || patient:*).

12. Safety Data

a. Adverse events

All events will be coded using the Medical Dictionary for Regulatory Activities (MedDRA). Type and incidence of all AEs will be tabulated. Severity and drug relatedness of all reported AEs will be tabulated.

b. Clinical Laboratory Tests

	Statistical Analysis Plan Protocol N. BIIT0215– Platinum	Pag. 14 di 18
---	---	---------------

For the clinical laboratory data, descriptive statistics will be generated for all tests performed. Laboratory abnormalities will be determined in accordance with the normal ranges of the clinical laboratory. Laboratory abnormalities will be tabulated.

13. Tables

The following tables will be repeated for each visit, if applicable.

- P1. Number and percentage of patients enrolled per center
- P2. Number and percentage of patients stratified by gender; mean and median age, range and interquartile range;

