P21. Number and percentage of patient who have correctly taken the prescribed doses of treatment within the last 28 days; if don't, mean and median, interquartile range and range of injections have not been performed during the last 28 days;

P22. Number and percentage of patients per reasons to non correctly taken the treatment:

- a) Anxiety for injection
- b) Skin reaction
- c) Forgot to take the dose
- d) Pain at the injection site

- e) Depression
- f) Headhache
- g) Fatigue
- h) Flu-like symptoms
- i) “I did not want to”
- j) “I am not sure of the benefits”
- k) “I am tired of injections”
- l) No one available for injection
- m) Uncomfortable dosing
- n) “I am pregnant / I have planned a pregnancy”
- o) Other

- P23. Mean and median, interquartile range and range of injections expected from the therapy taken in the last 28 days;
- P24. Mean and median, interquartile range and range of MSTCQ;
- P25. Change from baseline in the score of the MSTCQ at 12 and 24 weeks;
- P26. Adjusted repeated measures analysis of variance for change of the MSTCQ at 12 and 24 weeks;
- P27. Mean and median, interquartile range and range of MusiQol;
- P28. Change from baseline in the score of the MusiQol at 12 and 24 weeks;
- P29. Adjusted repeated measures analysis of variance for change of the MusiQol at 12 and 24 weeks;
- P30. Mean and median, interquartile range and range of FSS;
- P31. Change from baseline in the score of the FSS at 12 and 24 weeks;
- P32. Adjusted repeated measures analysis of variance for change of the FSS at 12 and 24 weeks;
- P33. Mean and median, interquartile range and range of EDSS;
- P34. Change from baseline in the score of the EDSS at 12 and 24 weeks;
- P35. ARR, Annualized Relapse Rate
- P36. Number and percentage of abnormalities in laboratory values per each test;
- P37. List of all laboratory abnormalities;
- P38. Number and percentage of adverse events stratified by severity;

	
Statistical Analysis Plan Protocol N. BIIT0215– Platinum
	
Pag. 18 di 18

--	---	---

- P39. List of all adverse events with related characteristics;
- P40. Number and percentage of patients who discontinued the study and reasons of discontinuity;
- P41. Number and percentage of patients who experienced pregnancy during the study and outcome of pregnancy.

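### SAP 11.b sends the 24-week change in ARR to a repeated measures ANOVA although relapse follow-up is unequal; a relapse count over observed time is needed

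*SAP*

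**What the plan says.** **Endpoint and method.** SAP 11.b includes among the secondary endpoints "Changes from baseline in clinical measures (ARR, percentage of relapse-free patients), measures at 24 weeks". It then states: "All the above primary and secondary endpoints will be analysed by a repeated measures analysis of variance adjusted for baseline factors". Protocol 16.3.4 likewise gives all other endpoints the same technique as the primary.

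**Missing data.** SAP 10 contrasts the mixed model with the ANOVA in these words: "Unlike the repeated measures ANOVA, which requires a complete balanced array of data". SAP 9 refers to scoring rules for three named questionnaires and adds: "For the other variables no imputation technique will be apply". ARR falls under that last sentence.

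**Follow-up.** Protocol 12.1 says: "Subjects discontinuing from study treatment for any of the abovementioned reasons must be permanently withdrawn from the study". The schedule in Protocol 4.2 records relapses and EDSS at T0, T1, T2 and ET only. One listed reason for stopping is "At the discretion of the Investigator for medical reasons". For patients lost to follow-up, 12.1 adds that "the ET visit form will have to be filled by the investigator also for patients that are lost to follow up".

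**Analysis set and output.** SAP 5 and Protocol 16.3.1 define the Full Analysis Set as every enrolled patient with at least one dose. SAP table P35 reads only "ARR, Annualized Relapse Rate". No section gives an ARR formula, a time at risk, an offset, or a rule for how ET data enter the week-24 value.

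**The concern.** An annualised relapse rate is a count divided by time observed. The ANOVA has no place for unequal time: it takes one number per patient per occasion and weights each equally. The plan guarantees unequal time, because stopping treatment ends relapse recording.

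If the SAP is followed literally, a treated patient without a week-24 value is left out of the analysis, and so is any relapse recorded at that patient's ET visit. This conflicts with the Full Analysis Set. Two ways around it are open to the analyst, and each has its own fault. Annualising each patient over the time actually followed gives very large values to short follow-up. Dividing every count by 24 weeks treats unobserved time as relapse-free.

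If some stops follow a relapse, leaving those patients out biases the rate downwards and annualising them individually biases it upwards. The SAP does not choose, so the choice could be made after the data are seen. Disease activity is a stated secondary objective, and SAP 1 says that the results are for publication.

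**Working it through.** The documents give no expected ARR, formula or power for this endpoint, so there is no stated figure to reproduce.

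**Inputs**
- 275 patients (SAP 6, Protocol 16.5).
- Planned follow-up 24 weeks (Protocol 7.2). With 365.25/7 = 52.18 weeks per year, this is 24/52.18 = 0.45995 years.
- Baseline relapse window 12 months (SAP 8).
- Assumption: a rate of 0.256 per year in patients other than the relapse-driven stoppers. This is the two-weekly arm of the earlier phase 3 trial (results table in Protocol 5.1).
- Assumption: k patients have one relapse and stop at week 6. The documents give no value for k, so it is varied.

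**Step 1. One relapse annualised over the patient's own follow-up: 52.18/weeks**
- stop at week 4: 13.0 per year
- week 8: 6.5
- week 12: 4.3
- week 20: 2.6
- completer, week 24: 2.2

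One relapse in the 12-month baseline window counts as 1.0. A single week-4 stopper adds 13.0/275 = 0.047 to the mean.

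**Step 2. Four ways to form the rate**
- Pooled: [(275 − k) × 0.256 × 0.45995 + k] / [(275 − k) × 0.45995 + k × 6/52.18]
- Completers only: 0.256
- Mean of individual rates: [(275 − k) × 0.256 + k × 52.18/6] / 275
- Fixed 24-week denominator: [(275 − k) × 0.256 × 0.45995 + k] / (275 × 0.45995)

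**Step 3. Results**

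k = 1:
- Pooled: (32.26 + 1)/(126.03 + 0.115) = 0.264
- Completers: 0.256, 3% below pooled
- Individual mean: (70.14 + 8.70)/275 = 0.287, 9% above pooled
- Fixed denominator: 33.26/126.49 = 0.263

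k = 5:
- Pooled: (31.79 + 5)/(124.19 + 0.575) = 0.295
- Completers: 0.256, 13% below pooled
- Individual mean: (69.12 + 43.48)/275 = 0.409, 39% above pooled
- Fixed denominator: 36.79/126.49 = 0.291

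k = 0: pooled, completers-only and individual mean all give 0.256.

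**Step 4. Is k = 5 plausible?** At 0.256 per year, 275 patients have about 275 × 0.256 × 6/52.18 = 8.1 relapses by week 6. Five relapse-driven stops by then would be 5/8.1 = 62% of them, so k = 5 is an extreme case.

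**Step 5. Simulation.** 4,000 trials were run with 275 patients, a true rate of 0.256 and about 10% total dropout. A given share of first relapses was followed by stopping one week later.
- Share 0%: completers 0.256, individual mean 0.256.
- Share 25%: completers 0.199, individual mean 0.387.
- Share 50%: completers 0.140, individual mean 0.525.
- Pooled person-time stayed at 0.255 to 0.256 and the fixed denominator at 0.242 to 0.243 throughout.

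With true rates of 0.2 and 0.4 and a share of 50%, completers gave 0.109 and 0.226, and individual means 0.413 and 0.814.

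**The case against.** The strongest reply is that the plan may never run this ANOVA. SAP 13 lists adjusted ANOVA tables for TSQM-9 convenience, MSTCQ, MusiQoL and FSS (P20, P26, P29, P32), but none for ARR. P35 is one plain line and could be a pooled rate. The same bullet in 11.b also names a percentage of patients, which is a group quantity. This is fair as far as it goes. However, the sentence in 11.b covers ARR without exception, the ANOVA cannot run on a group rate, and nothing says that P35 is pooled. The mixed model in SAP 10 is only mentioned as possibly useful, and it too would need a per-patient rate.

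Four stronger readings are tempting but not supported:

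- A reader might infer that a relapse before an early stop must be either dropped or inflated. A fixed 24-week denominator or a pooled P35 would do neither.
- A reader might infer that the relapse data are lost. They are not: relapses are recorded at ET, P15 tabulates exacerbations since the last visit, and P40 gives reasons for stopping. The fault lies in the analysis rule.
- A reader might infer that relapse commonly ends treatment. Relapse is not a listed stopping reason in 12.1; it could enter only through the investigator's medical discretion. Protocol 10.4 says patients can receive Plegridy with corticosteroids during relapses.
- A reader might infer that the ET form completed for lost patients adds relapse-free time. No section says that its date ends the time at risk.

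**Conclusion.** The concern holds as a fault in the analysis method. SAP 11.b applies to ARR a technique that cannot handle unequal observation time and that, by the SAP's own description, needs complete data. Followed as written, it omits treated patients who lack a week-24 value.

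The size is uncertain and may be small. With one relapse-driven stop at week 6, the completer value is 3% low and the individual mean 9% high. The 13% and 39% figures need five such stops and should be read as an extreme, not as an expectation. With none, there is essentially no bias in the mean. These figures rest on a borrowed rate of 0.256 and on an unknown share of relapses that lead to stopping.

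The effect is confined to one unpowered secondary endpoint. The primary analysis is untouched, and ARR is not among the five patient-reported parameters that the documents call efficacy. The change is still worth making, because the better method is standard and removes a choice among readings that can bias in opposite directions.

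**What to change.** In SAP 11.b, take ARR out of the sentence that sends all endpoints to the repeated measures ANOVA.

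In SAP 13, define P35 as total relapses divided by total patient-years of observation in all treated patients. Observation runs from first dose to T2 or to the ET examination. For patients lost to follow-up, it ends at the last visit or contact at which relapses were actually assessed.

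Compare this with the rate in the previous 12 months using a Poisson or negative binomial model on relapse counts, with log observation time as offset and clustering by patient.

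The cost is SAP wording and one standard count model on data already collected. No change to Protocol 12.1 is needed: relapses up to T2 or ET are enough to define the rate. Relapse recording after stopping would require a protocol amendment, which this repair does not justify.

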### **16.5. Sample Size Considerations**

Data for estimating the sample size were derived from studies reporting the distribution (mean value and standard deviation) of the TSQM-9 in MS patients treated with IFN (9). Assuming an average value of the overall convenience domain at baseline of 55 (SD=16) (9), with 250 subjects we have a power of 90% to detect a change of 3 points on the overall convenience domain (from 55 to 58) under the conservative hypothesis of a SD=16 (9) for the difference between baseline and week 12. However, by assuming a drop-out rate up to 10% during the study, we consider it appropriate to enrol a total of 275 patients.

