Data for estimating the sample size were derived from studies reporting the distribution (mean value and standard deviation) of the TSQM-9 in MS patients treated with IFN (9). Assuming an average value of the overall convenience domain at baseline of 55 (SD=16) (9), with 250 subjects we have a power of 90% to detect a change of 3 points on the overall convenience domain (from 55 to 58) under the conservative hypothesis of a SD=16 (9) for the difference between baseline and week 12. However, by assuming a drop-out rate up to 10% during the study, we consider it appropriate to enrol a total of 275 patients.

7. Software

The analysis will be performed using the software Stata version 14.0.

8. Variables for analysis

This section contains definitions and conventions that will be used for the analysis.

Demographic and baseline characteristics

Demographic (age, gender, education and employment) and medical information (disease duration, previous treatments, comorbidities and concomitant therapies, EDSS score and number of relapses in the previous 12 months) will be obtained at baseline.

Efficacy

Being this a health outcomes research study, the term efficacy refers to the assessment of the following patients' reported parameters, corresponding to the primary and secondary objectives of the study, and to the measurement of the related endpoints:

- overall treatment satisfaction;
- injection system satisfaction;
- adherence to treatment;
- health-related quality of life;
- fatigue.

All the endpoint-related questionnaires, described below, will be administered at baseline and after 12 and 24 weeks of treatment.

Primary variables

a) Patients' Satisfaction assessment

- *Abbreviated Treatment Satisfaction Questionnaire to Medication (TSQM-9)*

The TSQM Version 1.4 is a 14-item psychometrically robust and validated instrument consisting of four scales. The four scales of the TSQM include the effectiveness scale (questions 1 to 3), the side effects scale (questions 4 to 8), the convenience scale (questions 9 to 11) and the global satisfaction scale (questions 12 to 14). In the TSQM-9, the five items related to side effects of medication were not included, which creates a need to psychometrically assess the performance of the abbreviated instrument.

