- P3. Number and percentage of patients stratified by race;
- P4. Number and percentage of patients stratified by educational level;
- P5. Number and percentage of patients stratified by working status;
- P6. Mean and median age, range and interquartile range of time since diagnosis of SM;
- P7. Number and percentage of patients undergoing pharmacological treatment for MS by active substance; mean and median, interquartile range and range of the dose and distribution of the frequency of treatment administration;
- P8. Number and percentage of patients undergoing concomitant pharmacological treatment by active substance; mean and median, interquartile range and range of the duration;
- P9. Mean and median, range and interquartile range of the total number of relapses from the diagnosis;
- P10. Mean and median, interquartile range and range of the total number of relapses in the last year;
- P11. Number and percentage of patients stratified for relevant previous and / or concomitant diseases; if previous, mean and median, range and interquartile range of duration; if ongoing, number and percentage of the diseases being treated;
- P12. Number and percentage of patients stratified by outcome (not performed / normal / abnormal) to physical examination in relation to:
 - a) General appearance;
 - b) Skin;
 - c) Head, neck, thyroid;
 - d) Ear, nose, throat;
 - e) Muscolo-skeletal;
 - f) Respiratory;

- g) Heart;
- h) Peripheral vascular;
- i) Gastrointestinal
- j) Abdomen, liver;
- k) Renal and genitourinary
- l) Endocrine / Metabolic
- m) Neurologic;
- n) Mental status;
- o) Other;

P13. Mean and median, interquartile range and range of height, weight and bmi value

P14. Mean and median, interquartile range and range of temperature, respiration rate, heart rate, maximum and minimum blood pressure;

P15. Mean and median, range and interquartile range of the number of episodes of acute exacerbation since the last visit;

P16. Mean and median, interquartile range and range of EDSS score;

P17. Mean and median, interquartile range and range of TSQM-9, all domains: effectiveness, convenience and global satisfaction;

P18. Change from baseline in the score of convenience satisfaction domain of TSQM-9 at 12 weeks;

P19. Change from baseline in the score of all domains of the TSQM-9 at 24 weeks;

P20. Adjusted repeated measures analysis of variance for change of convenience satisfaction domain of TSQM-9 at 12 and 24 weeks;

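### Percentage relapse-free at week 24 is assigned to an ANOVA that needs complete data, so withdrawn patients fall out and relapses recorded before they left may be lost

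*SAP*

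**What the plan says.** The endpoint in SAP 11.b reads "Changes from baseline in clinical measures (ARR, percentage of relapse-free patients), measures at 24 weeks". The same section sends it, with all other primary and secondary endpoints, to a repeated measures ANOVA adjusted for age, sex, disease duration, previous treatment duration and EDSS. SAP 10 notes that this method needs a full set of measurements on every subject. It mentions a mixed model only as a possible addition.

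The analysis set is the FAS (SAP 5, protocol 16.3.1), which keeps anyone enrolled who was dosed at least once. On leaving, protocol 12.1 says: "Subjects discontinuing from study treatment for any of the abovementioned reasons must be permanently withdrawn from the study". The sample size is set "by assuming a drop-out rate up to 10% during the study" (protocol 16.5).

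On missing data, SAP 9 refers to the scoring rules for TSQM-9, MSTCQ and MusiQoL, and then says: "For the other variables no imputation technique will be apply". Relapse status is one of those other variables.

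Relapses are recorded at T0, T1, T2 and ET (protocol 4.2). In SAP 13, table P15 summarises the "range and interquartile range of the number of episodes of acute exacerbation since the last visit", and tables are repeated by visit where applicable. P9 and P10 cover relapses since diagnosis and in the last year, and P35 gives the annualized relapse rate (ARR). No table gives the percentage relapse-free.

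**The concern.** Whether a patient is relapse-free at week 24 depends on 24 weeks of observation. A patient who leaves earlier falls into one of two groups. If a relapse was recorded before leaving or at ET, the status is settled: not relapse-free. If none was recorded, the status is unknown from that point on, and the record is censored.

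The planned method separates neither group. With no imputation, no rule carrying an ET record to week 24, and a method that by the SAP's own account needs complete data, the default is a completers analysis inside a nominal FAS. Recorded relapses in leavers can then disappear from the result. The ANOVA compares means across time points. It does not deliver a percentage relapse-free with an interval, and the table list does not ask for one.

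At stake is one of the few disease-activity results in a single-arm study intended for publication. There is no control arm in which the same loss would occur, so a bias would go straight into the reported percentage.

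**Working it through.** **Inputs**
- 250 evaluable, 275 enrolled, drop-out up to 10% (protocol 16.5, SAP 6).
- Proportion relapsed at one year, 0.187, in the every-2-week arm of the earlier phase 3 trial (protocol 5.1). Applying it here is an assumption: that trial was 83% treatment-naive and did not include patients who had failed earlier MS treatment.
- Constant hazard over the year: an assumption.
- Number of relapsers among those who leave: an assumption, so several values are shown.

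**1. The plan's own figure.** 250 × 1.10 = 275 reproduces the enrolment target. (250 / 0.90 = 278; the difference does not matter here.) Ten per cent of 275 is 27.5, taken as 27 withdrawals, leaving 248 completers.

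**2. Size without any relapse assumption.** In a given dataset, counting all 27 withdrawals as relapsed or all as relapse-free changes the percentage by 27/275 = 9.8 points.

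**3. Illustrative level.** Hazard h = −ln(1 − 0.187) = 0.207 per year. Relapse by week 24: 1 − exp(−0.207 × 24/52) = 0.0911, or 25.1 of 275. Relapse-free at week 24 is 90.9%, with standard error √(0.909 × 0.091 / 275) = 1.7 points. Relapse-free at week 12 is 95.3%.

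**4. Scoring of withdrawals, d = 10%, leaving unrelated to relapse.**
- All counted as relapsed: 0.90 × 90.9% = 81.8%.
- Completers only: 90.9%.
- Observed status to an ET visit placed at week 12: 0.90 × 90.9% + 0.10 × 95.3% = 91.3%.
- All counted as relapse-free: 0.90 × 90.9% + 10% = 91.8%.

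**5. Completers only, when x of the 27 who leave have relapsed.** Estimate = 1 − (25.1 − x)/248. If every withdrawal is instead counted as relapsed, the estimate is 1 − (25.1 + 27 − x)/275.

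| x (assumed) | Completers only | All withdrawals as relapsed |
|---|---|---|
| 2.5 (unrelated: 27 × 0.0911) | 90.9% | 82.0% |
| 8 | 93.1% | 84.0% |
| 12 | 94.7% | 85.4% |

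At x = 12 the completers figure is 94.7 − 90.9 = 3.8 points too high, about 2.2 standard errors.

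**6. Other inputs** (withdrawals all as relapsed; completers only; all as relapse-free).
- Drop-out 5%, risk 0.187: 86.3%; 90.9%; 91.3%.
- Drop-out 10%, risk 0.10: 85.7%; 95.3%; 95.7%.
- Drop-out 10%, risk 0.291 (phase 3 placebo): 76.8%; 85.3%; 86.8%.
- Drop-out 10%, ARR 0.256 with Poisson counts: 80.0%; 88.9%; 90.0%.

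The level moves with the assumed risk. The width from scoring alone always equals the drop-out rate.

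**The case against.** The strongest case against is that the readings closest to the text hardly differ. Counting someone who left without a relapse as relapsed is itself an imputation, which SAP 9 excludes. Without that extreme, completers only, observed status to ET and all-as-relapse-free give 90.9%, 91.3% and 91.8%, a spread of 0.9 points against a standard error of 1.7. This stands: the 82% end is a bound, not a result the plan would report. It holds only if leaving is unrelated to relapse.

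Nothing in the documents shows that relapsers leave more often. Relapse is not a listed reason for discontinuation in protocol 12.1, and protocol 10.4 notes that corticosteroids can be given with Plegridy during relapses. The 8 and 12 of 27 are therefore scenarios. Equally, nothing excludes the link, since investigator judgement and consent withdrawal are both listed reasons.

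It can also be said that a relapse recorded at ET is not missing, so a no-imputation rule does not delete it. That is fair, and it is why the point is that such relapses may be dropped. Keeping them still needs a rule that the SAP does not give. The optional mixed model does not supply one.

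A reader might infer that P15 is the only relapse variable and that its T2 value leaves only weeks 12 to 24 in view, giving 95.3%. The documents do not support this. P9, P10 and P35 are also relapse outputs, and P15 is repeated by visit, so the T1 and T2/ET counts add up to weeks 0 to 24. What is missing is an instruction to add them.

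Finally, SAP 8 defines efficacy by patient-reported parameters, so this is part of one secondary item. That limits the weight of the point but does not answer it.

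**Conclusion.** The point holds. As written, percentage relapse-free at 24 weeks falls to a completers analysis despite the FAS label, relapses known before withdrawal may be lost, and the specified method and table list do not produce the named percentage.

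The size is about 10 points between the two extreme scorings at 10% drop-out. The span of about 82% to 92% rests on a borrowed one-year risk of 18.7% and a constant hazard, and is illustrative. Completers-only is about right, at 90.9%, if leaving is unrelated to relapse. It is biased upward otherwise: 93.1% or 94.7% under the assumed 8 or 12 relapsers among 27 withdrawals.

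A reader might join these figures into a range of 82% to 95% due to scoring choice alone. That goes too far: the top needs either an assumption about who leaves or omission of the T1 count, neither of which is a way of scoring withdrawals. Nor do the documents show that the plan will in fact overstate the percentage, only that it would if relapsers leave more often. The primary endpoint is not affected.

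**What to change.** In SAP 11.b:
- Define relapse-free as no relapse from first dose to week 24, adding the since-last-visit counts at T1 and T2/ET.
- Count any relapse recorded before withdrawal or at ET as an event.
- For this endpoint, replace the ANOVA with a Kaplan-Meier estimate at week 24 with its 95% CI in the FAS, censoring relapse-free leavers at last contact. The documents schedule the recording of relapses but do not confirm that onset dates are captured. If they are not, use a life table by visit interval.
- Add one sensitivity row that counts relapse-free withdrawals as relapsed.

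In SAP 13, add one table for the result.

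The cost is SAP wording and one table. No new visit is needed, because relapses are already recorded at T1, T2 and ET. The reported percentage may be slightly less favourable, and the covariate adjustment is dropped for this endpoint. Censoring still assumes that leaving carries no information about relapse; the sensitivity row bounds the effect of that assumption.
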